8.4.5. Physical Examination

Worst changes from baseline in physical examination (normal, abnormal but not clinically significant, and abnormal and clinically significant) will be summarized using shift tables. Physical examination records will be listed in detail.

8.4.6. ECOG Score

ECOG scores will be listed in detail for all subjects.

8.4.7. Echocardiography

Descriptive summary will be provided for left ventricular ejection fraction (LVEF) measured at each visit and their changes from baseline. Number and percentage of subjects in the following categories will be provided: LVEF from $40\% \sim 50\%$ or with $10\% \sim 19\%$ decrease from baseline, LVEF from $20\% \sim 39\%$ or with >20% decrease from baseline, and post-baseline LVEF < 20%.

Worst changes from baseline in valve function measurement (normal, abnormal but not clinically significant, and abnormal and clinically significant) will be summarized using shift tables.

Echocardiography records will be listed in detail.

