4. STUDY ENDPOINTS

4.1. Safety Variables

4.1.1. Adverse Events

Adverse events (AEs)

The definition of AEs can be found in the section 8.1 of protocol. AEs should be collected from the time of informed consent through follow-up. The follow-up period was 30 days (\pm 3 days) after discontinuation of study treatment. SAEs occurring during the follow-up period should be reported to the sponsor by routine methods.

Treatment emergent adverse events (TEAEs)

TEAEs are defined as adverse events that worsened or occurred following the first dose date of study treatment and within 30 days of the last treatment. If missing dates or time prevent a clear determination as to whether AE is treatment emergent, the adverse event will be regarded TEAE.

Treatment related adverse events

Treatment related AEs are defined as TEAEs definitely related, possibly related to study treatment, and the relationship unable to determine.

Serious adverse events (SAEs)

The definition of AEs can be found in the section 8.2 of protocol.

Treatment related SAEs

Treatment related SAEs are defined as SAEs definitely related, possibly related to study treatment, and the relationship unable to determine.

Adverse event of special interest (AESI)

According to the toxicological results of GFH018, ASEIs include elevated cardiac biomarkers BNP or troponin, and abnormal cardiac ultrasound.

Adverse events leading to interruption of study treatment

Adverse events leading to dose reduction of study treatment

Adverse events leading to discontinuation of study treatment

Severity of adverse events

Severity of all AEs will be graded according to CTCAE v5.0 with grade 1 to 5.

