8.4.2. Laboratory Evaluations

By-visit descriptive summary will be provided for hematology, blood biochemistry, urinalysis (quantitative measurements), coagulation, thyroid function, and their changes from baseline.

For hematology, blood biochemistry, coagulation, and cardiac markers, changes in CTCAE grade from baseline (Grade 0 to 4, where Grade 0 is non-missing value other than Grade 1-4) to worst CTCAE grade after treatment starts (Grade 0 to 4, where Grade 0 means normal) will be summarized using shift tables. Test results from both scheduled and unscheduled visits will be included. For the tests without corresponding CTCAE grades, results in shift tables will be categorized into "lower than normal values and higher than normal values (i.e., both higher than normal values and lower than normal values occurred after first dose of treatment)", "lower than normal values", "normal values", and "higher than normal values". CTCAE grading reference ranges for laboratory tests are detailed in Appendix I.

Qualitative descriptive summaries will be provided for urinalysis (qualitative) results measured at each visit. A shift table will also be provided by normal, abnormal without clinical significance, and abnormal with clinical significance. For urine protein, a shift table by CTCAE grade will also be provided.

Laboratory test results will be listed separately for hematology, urinalysis, coagulation, blood biochemistry, virology, thyroid function, cardiac markers, and pregnancy test.

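### SAP 8.4.7: the LVEF categories count a low value already present at entry in the same cell as a new fall, and LVEF has no shift table to separate them

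*SAP*

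**What the plan says.** SAP 8.4.7 plans four outputs for echocardiography.

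- **By-visit statistics for LVEF.** "Descriptive summary will be provided for left ventricular ejection fraction (LVEF) measured at each visit and their changes from baseline". Section 8.1 defines such a summary as n, mean, SD, median, minimum and maximum.
- **LVEF categories.** "Number and percentage of subjects in the following categories will be provided". Category 1 is LVEF of 40–50%, or a fall of 10–19%. Category 2 is LVEF of 20–39%, or a fall of more than 20%. Category 3 is an LVEF below 20%. The sentence ends "or with >20% decrease from baseline, and post-baseline LVEF < 20" (per cent), so the label post-baseline is attached to the third category only.
- **Valve function.** "Worst changes from baseline in valve function measurement (normal, abnormal but not clinically significant, and abnormal and clinically significant) will be summarized using shift tables". No such table is named for LVEF.
- **Listings** of all echocardiography records.

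Section 4.1.1 names the adverse events of special interest (AESIs) as "elevated cardiac biomarkers BNP or troponin, and abnormal cardiac ultrasound". For the other cardiac AESI measure, 8.4.2 does plan a shift: "For hematology, blood biochemistry, coagulation, and cardiac markers, changes in CTCAE grade from baseline" to the worst grade on treatment, using scheduled and unscheduled results. Shift tables are also planned for vital signs (8.4.3), ECG (8.4.4) and physical examination (8.4.5).

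**The concern.** A safety table of category counts is normally read as showing what happened on treatment. Here the absolute part of categories 1 and 2 asks only where the LVEF lies, not whether it moved. The count therefore mixes two kinds of subject: those whose LVEF fell, and those who came in with a value in the range and stayed there or improved. Because the counts are not crossed with the baseline category, the table itself gives no way to tell them apart.

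LVEF is the main numerical result of the echocardiogram, and an abnormal echocardiogram is one of this trial's AESIs. In cohorts of 3 to 6, one misread subject changes the displayed percentage a great deal.

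**Working it through.** The SAP states no rate or sample size for this table, so there is no figure to reproduce. The check is to apply the rule as written.

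**Inputs.** The three categories are from 8.4.7. Group sizes are from section 6: escalation cohorts of 3–6 and at least 12 subjects at the RP2D. Two points are not in the SAP and are treated as assumptions: the lowest LVEF allowed at entry (varied below) and an upper LVEF of 75% for the grid.

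**Step 1: example subjects.** The SAP does not say whether a fall is in percentage points (baseline − post) or relative (100 × (baseline − post) / baseline), so both are shown.

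| Baseline → post (%) | Change: points; relative | Category, points | Category, relative |
|---|---|---|---|
| 45 → 45 | 0; 0% | 1 | 1 |
| 45 → 48 | +3; +6.7% | 1 | 1 |
| 50 → 50 | 0; 0% | 1 | 1 |
| 38 → 38 | 0; 0% | 2 | 2 |
| 38 → 39 | +1; +2.6% | 2 | 2 |
| 65 → 53 | −12; −18.5% | 1 | 1 |
| 65 → 45 | −20; −30.8% | 1 | 1 and 2 |
| 65 → 43 | −22; −33.8% | 1 and 2 | 1 and 2 |
| 75 → 55 | −20; −26.7% | none | 2 |

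The first five subjects had no fall and are all counted, on either reading. The 65 → 53 subject, a real fall, shares category 1 with 45 → 45.

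Reading all three categories as post-baseline does not cure this: a subject at 45% throughout has a post-baseline value of 45%.

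**Step 2: dependence on the entry limit.** Take whole-number baseline and post-baseline values from the entry minimum to 75%, keep the pairs with no fall, and count those the rule puts in a category. With m values from the minimum to 75 there are m(m+1)/2 no-fall pairs. With k values from the minimum to 50, k(k+1)/2 of them are counted.

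| Assumed entry minimum | No-fall pairs counted |
|---|---|
| 40% | 11×12/2 = 66 of 36×37/2 = 666 |
| 45% | 6×7/2 = 21 of 31×32/2 = 496 |
| 50% | 1 of 26×27/2 = 351 (only 50 → 50) |
| 51% | 0 of 25×26/2 = 325 |

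These are counts of possible pairs, not expected numbers of patients. They show where the problem vanishes.

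**Step 3: weight of one such subject.** 1/3 = 33.3%, 1/6 = 16.7%, 1/12 = 8.3%.

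**Step 4: other loose ends in the same sentence**, which a redraft should settle.

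- A fall of exactly 20%, or between 19% and 20%, meets neither fall criterion. In points, 75 → 55 lands in no category.
- A subject can meet two categories (65 → 43), with no rule for which one counts.
- A value between 39% and 40% lies in neither absolute range.

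**The case against.** The strongest reply is that this is a request for one more table, not an error of consequence.

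- **The size rests on an unseen limit.** An unchanged subject is counted only if entry admitted an LVEF of 50% or less. That limit belongs to the protocol. This stands, and it may reduce the problem to nothing.
- **Other outputs show the change.** By-visit changes from baseline are planned, and their minimum shows the largest fall at each visit. Listings separate 50 → 50 from 65 → 45 at once in a cohort of 3 to 6. This stands, so it would be wrong to say that LVEF change from baseline goes unreported. What these outputs do not give is how many subjects fell, and from which baseline category.
- **The adverse event tables are protected.** A reader might infer that the AESI or cardiac toxicity rate is inflated. The SAP does not support that: summary tables hold only treatment-emergent events (8.4.1), which must begin or worsen after the first dose (4.1.1).
- **No decision hangs on this count.** A reader might also infer that dose selection could be distorted, or that a real fall could be dismissed as pre-existing. Section 3 bases escalation mainly on DLTs, adverse events of grade 2 and above, and PK and pharmacodynamic data, and the RDE on the data as a whole. Section 5 says no hypothesis is tested. Nothing ties a decision to this table.
- **Shift tables are not universal in the SAP.** Thyroid function is not named for one in 8.4.2, and ECOG is only listed (8.4.6). Table 5 also joins an absolute QTcF value to a change by 'or'. So no stated rule is broken. But the ECG section pairs that criterion with a shift table, which is exactly what LVEF lacks.

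The replies limit the consequence. They do not change what the category rule counts.

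**Conclusion.** The point holds as a minor defect of one table. As written, categories 1 and 2 in 8.4.7 count subjects whose LVEF was already in range at entry and did not fall, together with subjects who had a new fall, and no LVEF shift table separates them. By-visit changes, listings and the treatment-emergent and AESI tables are not affected.

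Each such subject shifts the displayed percentage by 8.3 to 33.3 points, depending on group size. That is simply the weight of one subject; the number of such subjects cannot be derived from the SAP. If entry required at least 50%, only a baseline of exactly 50% is affected; if it required more than 50%, nobody is. The finding on the rule itself does not depend on whether a fall is read in points or as relative percent.

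**What to change.** In 8.4.7:

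1. State that all LVEF categories use post-baseline values, including unscheduled echocardiograms, as 8.4.2 already does for laboratory results.
2. Add a shift table of baseline LVEF category to worst post-baseline category, with contiguous bounds (for example >50%, 40% to ≤50%, 20% to <40%, <20%) and each subject counted once, in the worst category. A subject who stays in the entry category then sits on the diagonal and is no longer read as a new case.
3. Report the fall from baseline as a separate count. Say whether it is in percentage points or relative percent, and close the gap between the 10–19% band and the band above 20%.

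The cost is a few lines of SAP wording and one extra table. No new data are needed.

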8.4.3. Vital Signs

By-visit descriptive summary will be provided for vital sign measurements (body temperature, heart rate, respiratory rate, systolic and diastolic blood pressure) and their changes from baseline. Changes from baseline to worst post-baseline measurements will be summarized in shift table according to the table below (Table 4). The number and percentage of subjects with significant changes in vital sign measurements will be summarized for each group.

Table 4 Criteria for Significant Changes in Vital Signs from Baseline

	Above Normal	Below Normal
Systolic Blood Pressure (mmHg)	increase $>$ = 20 from baseline, and $>$ = 160	Decrease $> = 20$ from baseline, and $< = 80$
Diastolic Blood Pressure (mmHg)	increase $>$ = 15 from baseline, and $>$ = 100	Decrease $> = 15$ from baseline, and $< = 50$
Heart Rate (beats/min)	increase $>$ = 15 from baseline, and $>$ = 100	Decrease $> = 15$ from baseline, and $< = 60$
Respiratory rate (breaths/min)	> 24	< 8
Body Temperature (°C)	>= 39.1	-

Vital signs for each subject will be listed in detail, and values with significant changes from baseline will be flagged.

8.4.4. 12-Lead Electrocardiogram

Descriptive summaries will be provided for each electrocardiogram (ECG) parameter measured at each visit and their corresponding changes from baseline (averaged over the three measurements).

According to Table 5, the number and percentage of subjects with abnormal changes in ECG parameters after treatment start will be summarized, and summaries will be provided in shift table for the worst change from baseline. ECG results for each subject will be listed in detail.

Table 5 Criteria for Significant Changes in ECG Indicators from Baseline

	Above Normal	Below Normal
QTcF (ms)	> 450 and $<$ = 480	-
	> 480 and $<$ = 500	-
	> = 501, or $>$ 60 increase from baseline	-
QT (ms)	> 450 and < = 480	-
	> 480 and $<$ = 500	-
	>= 501, or > 60 increase from baseline	-
Heart Rate (beats/min)	> 25% increase from baseline and value >= 100	> 25% decrease from baseline and value <= 50
PR (ms)	> 25% increase from baseline and value > 200	> 25% decrease from baseline and value < 120

	Above Normal	Below Normal
QRS (ms)	> 25% increase from baseline and value > 110	-

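### Three rules for descriptive safety tables fail as written: the LVEF fall bands skip 20%, Grade 0 has two meanings in one shift table, and the lymphocyte-increased Grade 2 range is reversed

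*SAP*

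**What the plan says.** **LVEF (SAP 8.4.7).** The section introduces its table with "Number and percentage of subjects in the following categories will be provided". The first category is an LVEF of 40% to 50%, "or with $10\% \sim 19\%$ decrease from baseline". The second starts with a level band, "LVEF from $20\% \sim 39" percent; its fall limit and the third category then read "or with >20% decrease from baseline, and post-baseline LVEF < 20" percent. The section does not say whether the fall is in points or relative percent, or how to count a subject who meets two categories.

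**Grade 0 (SAP 8.4.2).** The laboratory shift tables cross baseline grade with worst grade after treatment starts. On the baseline axis, "Grade 0 is non-missing value other than Grade 1-4". On the post-baseline axis the scale is "Grade 0 to 4, where Grade 0 means normal". For the results that feed the table, "Test results from both scheduled and unscheduled visits will be included". A low/normal/high classification is offered only for tests that have no CTCAE grade.

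**Lymphocytes (SAP Appendix I).** Lymphocyte count increased, Grade 2, has 20,000/mm3 as its lower bound and 4000/mm3 as its upper bound. The same row in 10^9/L runs from 20 to 4. Grade 3 is above 20,000/mm3.

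**The concern.** These are programming rules. Applied literally, each puts some results in the wrong place or in none. The LVEF rule is not monotone: as the fall grows, a subject can pass from the milder category to no category and then to the second. The two Grade 0 definitions differ wherever Appendix I leaves an abnormal value ungraded, and it does so by design when the baseline is abnormal. The lymphocyte row, in mm3, defines an empty set.

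Safety is a primary objective (SAP section 2) and abnormal cardiac ultrasound is an adverse event of special interest (section 4.1.1), so the LVEF table will be read closely. Hepatocellular carcinoma and cholangiocarcinoma are among the expansion tumor types (section 3), so abnormal baseline liver tests are plausible.

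**Working it through.** **1. LVEF bands.** Inputs are the limits in 8.4.7. With baseline b and post-baseline value v, the fall is d = b − v (points) or d = 100(b − v)/b (relative).

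- First category: 40 ≤ v ≤ 50, or 10 ≤ d ≤ 19.
- Second category: 20 ≤ v ≤ 39, or d > 20.
- Third category: v < 20.

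Any d with 19 < d ≤ 20 fails both fall conditions.

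| b to v | Reading | d | Category |
|---|---|---|---|
| 75 to 56 | points | 19 | first |
| 75 to 55 | points | 20 | none |
| 75 to 54 | points | 21 | second |
| 75 to 61 | relative | 14/75 = 18.7% | first |
| 75 to 60 | relative | 15/75 = 20.0% | none |
| 75 to 59 | relative | 16/75 = 21.3% | second |

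Fixing the unit therefore does not close the gap.

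For scale, assume whole-number baselines of 50 to 75; the SAP gives no range. There are then 26 pairs with a fall of exactly 20 points:

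- 71 to 51 through 75 to 55: no category (5 pairs).
- 60 to 40 through 70 to 50: first category only, by level (11 pairs).
- 50 to 30 through 59 to 39: second category, by level (10 pairs).
- Check: 5 + 11 + 10 = 26.

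On the relative reading, 10 whole-number pairs have a fall above 19% and up to 20% and no category, for example 65 to 52 (13/65 = 20.0%). If percentages are first rounded to whole numbers, on which the SAP is silent, 5 remain. The pairs with v from 20 to below b number 30 + 31 + … + 55 = 26 × 42.5 = 1,105.

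If LVEF is recorded with decimals, values between 39% and 40% are outside both level bands. From 49 to 39.5 the fall is 9.5 points, or 9.5/49 = 19.4%, and neither reading gives a category.

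**2. Grade 0.** Inputs are the two definitions in 8.4.2 and the ALT rows of Appendix I, where Grade 1 with an abnormal baseline starts at 1.5 × baseline.

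- Take baseline ALT 4.0 × ULN. Grade 1 starts at 1.5 × 4.0 = 6.0 × ULN.
- Later values of 4.0, 5.8 and 3.5 × ULN are all below 6.0, so ungraded, and all above ULN, so not normal. The baseline definition would give Grade 0; the post-baseline definition gives no cell.
- With one later value of 0.9 × ULN the subject has a normal result and is Grade 0. With a later value of 6.0 × ULN the subject is Grade 1.

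A subject lacks a cell only if every post-baseline result is ungraded and none is normal. Eosinophils above ULN that never exceed baseline behave the same way, because Appendix I grades them only when both limits are exceeded. ALT and eosinophils have CTCAE grades, so the low/normal/high fallback does not apply to them.

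**3. Lymphocytes.** The condition 20,000 ≤ x < 4000 has no solution. As printed in mm3, a count between 4000 and 20,000 receives no increased grade, while a count above 20,000 is Grade 3.

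**The case against.** Much of the case on the other side stands.

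- **The 39% to 40% gap** exists only if LVEF is recorded with decimals, which the SAP does not say.
- **Unit and overlap** are clarifications, not errors. Points is the more natural reading, since percent is the unit of LVEF itself. Table 5 in section 8.4.4 uses percent for relative change, as in "> 25% increase from baseline and value > 110", but there the measurements are in ms or beats/min, so it says little about LVEF. Overlapping categories can legitimately be reported if that is intended.
- **Grade 0.** On the post-baseline axis, normal may be shorthand for not graded. Subjects could drop out only on the literal reading, and only when every later result is abnormal and ungraded. But the sentence gives two different definitions, and a programmer should not have to choose.
- **Appendix I as read from PDF** is visibly damaged in places, so the inequality signs in the lymphocyte row might be misread. The 10^9/L form also runs high to low, which favours an error in the source. This is not conclusive, because the lymphocyte-decreased rows use the same high-to-low layout and the increased form can be read as 4 to 20. The source table should be checked first.
- **Total cholesterol.** Four ascending ranges carry the labels 1, 2, 2, 3. A reader might infer a grading error, but nearby grade labels are displaced by extraction, so this is only a note to check the source.
- **The counts of pairs** describe a grid under an assumed baseline range. They are not patient frequencies.

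None of this removes the gap at a 20% fall, the double definition of Grade 0, or the unmeetable mm3 range as printed.

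**Conclusion.** The point holds as a minor correction to three stated rules. The LVEF gap is certain from the text on either reading of the fall. The Grade 0 conflict is certain in wording, but its effect depends on literal programming. The lymphocyte row is wrong as printed, subject to a check of the source.

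On the assumed grid, 5 (points) or 10 (relative) of 1,105 possible pairs are left uncategorised by the gap at a 20% fall. The document gives no figures from which to estimate how many subjects would be affected.

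A reader might infer that large LVEF falls would go unreported, that cardiac events of special interest would be missed, or that a dose decision could change. The SAP does not support this. Section 8.4.7 also provides LVEF change from baseline by visit and full echocardiography listings. Section 8.4.1 tabulates and lists AESIs and DLTs separately, and AE severity follows CTCAE v5.0 (section 4.1.1). Only the LVEF category table and the laboratory shift tables are affected.

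**What to change.** - **8.4.7.** Make the bands contiguous: a fall of at least 10 and below 20, then at least 20; LVEF 40 to 50, then at least 20 and below 40. In the same edit, state the unit of the fall and that each subject is counted once, in the worst post-baseline category.
- **8.4.2.** Use the baseline definition of Grade 0 (not missing and not graded 1 to 4) on both axes. A footnote should say that Grade 0 then means ungraded, not necessarily normal.
- **Appendix I.** Check the source table, then put the lymphocyte-increased Grade 2 bounds in ascending order in both units, so that the grade meets Grade 3. Make this change together with the Grade 0 change; otherwise a count of 10,000/mm3 would be shown as Grade 0. Check the cholesterol labels at the same time against the CTCAE v5.0 that the SAP names.

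The cost is a few sentences and minor programming, best done before database lock. On the same assumed grid, the new bands change the worst category in 16 of 1,105 pairs on the points reading (the 5 uncategorised plus the 11 held in the milder category). On the relative reading they change 13: the 10 uncategorised plus 50 to 40, 55 to 44 and 60 to 48, which are exact 20% falls now placed by level. Every change is to a more severe category or from none to a category.

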8.5. Efficacy Analysis

Efficacy analyses will be performed for subjects in the FAS based on RECIST evaluation.

A waterfall plot will be presented for the best percentage change from baseline in the sum of target lesion diameters. Swim plots will be prepared for all subjects to present subject drug exposure and efficacy evaluations at each visit.

The best overall response (BOR) will be determined and statistically analyzed based on evaluations at all visit, and the number and percentage of subjects with BOR of CR, PR, SD, PD, NE, and Non-CR/Non-PD will be summarized. Participants with BOR of unknown or none (i.e. no valid record of post-baseline tumor assessments) will be considered non-responsive. ORR (CR or PR) and DCR (CR, PR or SD) will be calculated based on BOR, respectively, and the Clopper-pearson method will be used to estimate ORR and DCR and their 2-sided 90% confidence intervals.

Time to progression (TTP), duration of response (DOR), and progression-free survival (PFS) will be analyzed using the Kaplan-Meier method, with their median and 90% confidence interval will be provided. If the number of subjects in a group is less than 10, only DOR, TTP and PFS listings will be provided for each subject.

Assessments of target lesion, non-target lesion, new lesion, and overall response will be listed in detail for each subject and each visit.

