4.2. Efficacy Variables

The clinical efficacy will be evaluated by investigator per RECIST (Response Evaluation Criteria in Solid Tumors) 1.1. The efficacy variables including:

- Best overall response (BOR) is defined as the best overall response recorded from the start of treatment until disease progression or the last tumor assessment, whichever occurs earlier.
- Overall response rate (ORR) is defined as the proportion of subjects with BOR of complete response (CR) or partial response (PR).
- Disease control rate (DCR) is defined as the proportion of subjects with a BOR of CR, PR, or stable disease (SD).
- Duration of response (DOR) is defined as the time from first evidence of CR or PR to disease progression or death from any cause, whichever occurs first.

- Progression free survival (PFS) is defined as the time from start of study treatment until disease progression or death from any cause, whichever occurs first.
- Time to progression (TTP) is defined as the time from start of study treatment until disease progression.

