7.2. Full Analysis Set (FAS)

FAS: consists of all subjects who have received at least one dose of study treatment.

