8. STATISTICAL METHOD

8.1. General Statistical Consideration

The statistical analysis plan be finalized prior to data base lock. All analyses and data presentations will be generated using SAS® Version 9.4 or higher software

Descriptive summary

Continuous variables: Descriptive statistics will include the number of non-missing values (n), arithmetic mean, standard deviation (SD), median, minimum and maximum values.

The minimum and maximum values will be displayed to the same decimal precision as the source data, the arithmetic mean and median values will be displayed to one more decimal than the source data, and the SD value will be displayed to two more decimals than the source data for the specific variable.

Categorical variables: Descriptive statistics will include counts and percentages per category. The denominator in all percentage calculations will be the number of participants in the relevant analysis set, unless otherwise specified. Percentages will be displayed to one decimal place with the following exceptions: 1) percentages will not be displayed for zero frequencies; 2) percentages will be displayed as "100%" when percentage is 100%.

ORR and DCR will be calculated, the corresponding two-sided 90% confidence intervals will be estimated by the Clopper-Pearson method.

Baseline

Baseline is defined as the last non-missing measurement collected on or before first study drug administration. For ECGs, the average of the ECG parameters should be used.

Censor rule

Table 3 below shows the censor rule for PFS:

Table 3 Censor rule for PFS

No.	Situation	Event or Censor / Analyais date
1	PD or death	Event / PD date or death date
2	Have at least one post-baseline assessment, no PD, no Death	Censor / Last imaging date
3	No post-baseline assessment and no Death	Censo r/ First dosing date

Only subjects with the BOR of CR or PR will be included for DOR analysis. DOR will apply the same consor rule as PFS.

Best overall response (BOR) is the best measured response at any time post treatment. Subject without any post-treatment assessments will be treated as non-responder.

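### DCR counts only CR, PR and SD over all treated subjects, so any subject whose BOR is Non-CR/Non-PD would be counted with PD and NE

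*SAP*

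**What the plan says.** Four parts of the SAP together determine how DCR is computed.

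- **Numerator.** Section 4.2 defines DCR as "the proportion of subjects with a BOR of CR, PR, or stable disease (SD". Section 8.5 repeats it: "DCR (CR, PR or SD) will be calculated based on BOR".
- **BOR categories.** Section 8.5 plans that "the number and percentage of subjects with BOR of CR, PR, SD, PD, NE, and Non-CR/Non-PD will be summarized". Non-CR/Non-PD is therefore a separate category from SD.
- **Analysis set.** Section 8.5: "Efficacy analyses will be performed for subjects in the FAS based on RECIST evaluation". Section 7.2: "FAS: consists of all subjects who have received at least one dose of study treatment". There is no condition on measurable disease or target lesions.
- **Denominator.** Section 8.1: "The denominator in all percentage calculations will be the number of participants in the relevant analysis set, unless otherwise specified". Nothing different is specified for DCR.

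The only special handling in 8.5 concerns subjects whose BOR is unknown or absent, who count as non-responsive. No section maps Non-CR/Non-PD to SD, adds it to the DCR numerator, or removes such subjects from the denominator.

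**The concern.** A rate called disease control is normally read as the share of subjects whose disease did not progress at best assessment. A CR/PR/SD numerator delivers that when every non-progressing non-responder falls under SD. This SAP divides that group in two by giving Non-CR/Non-PD its own category, and the DCR definition does not follow the division.

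A subject recorded as neither CR nor PD would then carry the same weight in DCR as a subject with PD. PFS treats that state differently: under Table 3 in section 8.1 only progression or death is an event, so an assessment of Non-CR/Non-PD leaves the subject progression-free at that date.

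What is at stake is the reading of a secondary efficacy rate in small groups. Section 6 plans 6 to 12 subjects per treatment in expansion and at least 12 in the RP2D cohort, so one or two subjects move the rate visibly.

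**Working it through.** The SAP gives no DCR figure, assumed rate or power, so there is nothing of its own to reproduce. The check has a logical step and an illustration of size.

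**Step 1: where each BOR category goes under the rules as written.**

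| BOR category (8.5) | In denominator (7.2, 8.1) | In DCR numerator (4.2, 8.5) |
|---|---|---|
| CR, PR, SD | yes | yes |
| Non-CR/Non-PD | yes | no |
| PD | yes | no |
| NE | yes | no |

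Non-CR/Non-PD ends up with PD and NE.

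**Step 2: effect per subject.** Let n be the group size, x the number with CR, PR or SD, and k the number with Non-CR/Non-PD.

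- As written: DCR = x/n, whatever k is.
- Counting them as controlled: DCR = (x + k)/n.
- Difference: k/n, that is 1/n per subject.

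For one subject this is 1/12 = 8.3 points at n = 12 (the RP2D minimum in section 6) and 1/6 = 16.7 points at n = 6 (the smallest planned expansion group).

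**Step 3: illustration with the SAP's interval.** The intervals are two-sided 90% Clopper-Pearson, as in 8.1 and 8.5, with n = 12. The values of x and k are assumptions, not SAP figures.

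| x | k | DCR as written (90% CI) | Counting Non-CR/Non-PD (90% CI) |
|---|---|---|---|
| 4 | 0 | 4/12 = 33.3% (12.3–60.9) | 4/12 = 33.3% (12.3–60.9) |
| 4 | 1 | 4/12 = 33.3% (12.3–60.9) | 5/12 = 41.7% (18.1–68.5) |
| 4 | 2 | 4/12 = 33.3% (12.3–60.9) | 6/12 = 50.0% (24.5–75.5) |
| 4 | 3 | 4/12 = 33.3% (12.3–60.9) | 7/12 = 58.3% (31.5–81.9) |
| 6 | 2 | 6/12 = 50.0% (24.5–75.5) | 8/12 = 66.7% (39.1–87.7) |

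The row with k = 0 shows that nothing changes if no subject falls in the category. Taking such subjects out of the denominator would give a third answer: for x = 4 and k = 2, 4/10 = 40.0% (15.0–69.6).

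**The case against.** The case for leaving the text alone has real substance.

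- **No contradiction.** Sections 4.2 and 8.5 give the same definition. A frequency table can list categories that a derived rate does not count; PD and NE are listed and not counted either. This stands: the sections do not conflict. The fault is that one consistently stated rule treats one category in a way the name of the rate does not suggest.
- **No such subject may exist.** Eligibility is in the protocol, which is not at hand. The category may simply mirror the possible response values, and the waterfall plot of target lesion diameters is planned without any provision for subjects who have no target lesions. This also stands. It limits the size of the point but does not settle the rule for a category that the SAP chose to report.
- **Nothing is hidden.** The number with Non-CR/Non-PD will be tabulated and responses will be listed by subject and visit, so a reader can redo the sum. True, but the headline DCR and its interval would still be those of the narrower count.
- **Other remedies would also close the gap.** DCR could be restricted to subjects with measurable disease, or the SAP could say that the exclusion is deliberate. Either would be clear; at present the SAP does neither.

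A reader might infer that DCR in this trial is biased downward, or that DCR differences between groups will reflect the share of non-measurable disease rather than the drug. The SAP does not support either inference. The calculation estimates exactly the proportion that 4.2 defines, and the SAP gives no information on how many such subjects there are or how they are spread across groups.

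**Conclusion.** The point holds in conditional form. If a subject has a BOR of Non-CR/Non-PD, the plan followed to the letter leaves that subject in the DCR denominator and counts the subject with PD and NE. The cost is 1/n per subject compared with counting the subject as controlled: 8.3 points at n = 12 and 16.7 points at n = 6.

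This rests on two assumptions. The SAP does not define Non-CR/Non-PD, so the label is read at face value as neither complete response nor progression. The number of such subjects is unknown and may be zero.

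The impact is modest. Preliminary efficacy is a secondary objective (section 2), section 5 states that no hypothesis is tested, and no decision threshold for DCR appears in the SAP. The ORR numerator is not affected.

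**What to change.** In sections 4.2 and 8.5, define DCR as the proportion of subjects with a BOR of CR, PR, SD or Non-CR/Non-PD. State that Non-CR/Non-PD remains a non-response for ORR. Report the CR/PR/SD-only rate, with its 90% Clopper-Pearson interval, beside the new DCR as a sensitivity figure.

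The cost is a short wording change in two sections, one line in the DCR derivation and one extra row in the table. The downside is a slightly less strict DCR, which the sensitivity row makes visible. The change should be made before database lock, by which time section 8.1 requires the SAP to be final.
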